## **Supportive analyses**

Commercially Confidential Information

### **12.5 Analysis of secondary endpoints**

#### **12.5.1 Efficacy and/or Pharmacodynamics endpoint(s)**

Commercially Confidential Information

Commercially Confidential Information

### **12.5.2 Safety endpoints**

For all safety analyses, the safety set will be used. All listings and tables will be presented by treatment group.

Safety summaries (tables, figures) include only data from the on-treatment period with the exception of baseline data which will also be summarized where appropriate (e.g. change from baseline summaries). In addition, a separate summary for death including on treatment and post treatment deaths will be provided. In particular, summary tables for AEs will summarize only on-treatment events, with a start date during the on-treatment period (treatment-emergent AEs).

The on-treatment period lasts from the date of first administration of study treatment to 30 days after the date of the last actual administration of any study treatment.

#### **Adverse events**

All information obtained on AEs will be displayed by treatment group and subject.

The number (and percentage) of subjects with treatment emergent AEs (events started after the first dose of study medication or events present prior to start of double-blind treatment but increased in severity based on preferred term) will be summarized in the following ways:

- by treatment, primary system organ class and preferred term;
- by treatment, primary system organ class, preferred term and maximum severity;
- by treatment, Standardized MedDRA Query (SMQ) and preferred term.

Separate summaries will be provided for study medication related AEs, death, SAEs, other significant AEs leading to discontinuation.

The incidence of psychotomimetic AEs will be tabulated by treatment group, according to severity and relationship to drug.

A subject with multiple AEs within a primary system organ class is only counted once towards the total of the primary system organ class.

#### **Vital signs**

All vital signs data will be listed by treatment group, subject, and visit/time and if ranges are available, abnormalities as well as clinical notable values will be flagged. Summary statistics will be provided by treatment and visit/time.

#### **ECG evaluations**

All ECG data will be listed by treatment group, subject and visit/time; abnormalities will be flagged. Summary statistics will be provided by treatment and visit/time.

### **Clinical laboratory evaluations**

All laboratory data will be listed by treatment group, subject, and visit/time and if normal ranges are available abnormalities will be flagged. Summary statistics will be provided by treatment and visit/time. Shift tables using the low/normal/high/ (low and high) classification will be used to compare baseline to the worst on-treatment value.

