5. action taken regarding with study treatment.

All adverse events must be treated appropriately. Treatment may include one or more of the following:

- Dose not changed
- Dose Reduced/increased
- Drug interrupted/withdrawn

6. its outcome.

Conditions that were already present at the time of informed consent should be recorded in medical history of the subject.

Adverse events (including lab abnormalities that constitute AEs) should be described using a diagnosis whenever possible, rather than individual underlying signs and symptoms.

Adverse event monitoring should be continued for at least 30 days following the last dose of study treatment.

Once an adverse event is detected, it must be followed until its resolution or until it is judged to be permanent (e.g. Continuing at the end of the study), and assessment must be made at each visit (or more frequently, if necessary) of any changes in severity, the suspected relationship to the interventions required to treat it, and the outcome.

Information about adverse drug reactions for the investigational drug can be found in the Investigator Brochure (IB).

Abnormal laboratory values or test results constitute adverse events only if they fulfill at least one of the following criteria:

- they induce clinical signs or symptoms
- they are considered clinically significant
- they require therapy

Clinically significant abnormal laboratory values or test results must be identified through a review of values outside of normal ranges/clinically notable ranges, significant changes from baseline or the previous visit, or values which are considered to be non-typical in subjects with the underlying disease.

Follow the instructions found in the SOM for data capture methodology regarding AE collection for subjects that fail screening.

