### 10.2.1 Liver safety monitoring

To ensure subject safety and enhance reliability in determining the hepatotoxic potential of an investigational drug, a standardized process for identification, monitoring and evaluation of liver events has to be followed.

The following two categories of abnormalities / adverse events have to be considered during the course of the study (irrespective of whether classified/reported as AE/SAE):

- Liver laboratory triggers, which will require repeated assessments of the abnormal laboratory parameter
- Liver events, which will require close observation, follow-up monitoring and completion of the standard base liver CRF pages

Please refer to [Table 16-1](#) in Appendix 1 for complete definitions of liver laboratory triggers and liver events.

Every liver event defined in [Table 16-1](#) should be followed up by the investigator or designated personnel at the trial site, as summarized below. Additional details on actions required in case of liver events are outlined in [Table 16-2](#). Repeat liver chemistry tests (ALT, AST, TBL, PT/INR, ALP and G-GT) to confirm elevation.

- These liver chemistry repeats will be performed using the central laboratory. If results will not be available from the central laboratory, then the repeats can also be performed at a local laboratory to monitor the safety of the subject. If a liver event is subsequently reported, any local liver chemistry tests previously conducted that are associated with this event should have results reported on the unplanned local laboratory CRF
- If the initial elevation is confirmed, close observation of the subject will be initiated, including consideration of treatment interruption if deemed appropriate.
- Discontinuation of the investigational drug (refer to [Section 9.1.1](#)), if appropriate
- Hospitalization of the subject if appropriate
- Causality assessment of the liver event
- Thorough follow-up of the liver event should include
  - These investigations can include based on investigator's discretion: serology tests, imaging and pathology assessments, hepatologist's consultancy; obtaining more detailed history of symptoms and prior or concurrent diseases, history of concomitant drug use, exclusion of underlying liver disease

All follow-up information, and the procedures performed must be recorded as appropriate in the CRF.

Refer to the SOM for additional details.

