### **10.2.2 Renal safety monitoring**

The following two categories of abnormal renal laboratory values have to be considered during the course of the study:

- Serum creatinine increase  $\geq 25\%$  compared to baseline during normal hydration status
- Urine protein-creatinine ratio (PCR)  $\geq 1\text{g/g}$  or  $\geq 100\text{ mg/mmol}$ , OR new onset dipstick proteinuria  $\geq 3+$  OR new onset dipstick hematuria  $\geq 3+$  (after excluding menstruation, UTI, extreme exercise, or trauma)

Renal event findings must be confirmed 24-48 hours after the first assessment.

Every renal laboratory trigger or renal event as defined in [Table 16-3](#) should be followed up by the investigator or designated personnel at the trial site as summarized in [Section 16.2](#).

Refer to the SOM for additional details.

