## 16.2 Appendix 2: Specific Renal Alert Criteria and Actions and Event Follow-up

**Table 16-3 Specific Renal Alert Criteria and Actions**

Renal Event	Actions
Confirmed serum creatinine increase 25 – 49%	
 
Consider causes and possible interventions
 
Follow up within 2-5 days
 

Serum creatinine increase $\geq 50\%$ † OR if <18 years old, eGFR <math>\leq 35</math> mL/min/1.73 m^2	
 
Consider causes and possible interventions
 
Repeat assessment within 24-48h if possible
 
Consider drug interruption or discontinuation unless other causes are diagnosed and corrected
 
Consider patient hospitalization and specialized treatment
 

New onset dipstick proteinuria $\geq 3+$ OR Protein-creatinine ratio (PCR) $\geq 1\text{g/g}$ Cr (or mg/mmol equivalent as converted by the measuring laboratory)	
 
Consider causes and possible interventions
 
Assess serum albumin & serum total protein
 
Repeat assessment to confirm
 
Consider drug interruption or discontinuation unless other causes are diagnosed and corrected
 

New onset hematuria $\geq 3+$ on urine dipstick	
Assess & document
 
 
Repeat assessment to confirm
 
Distinguish hemoglobinuria from hematuria
 
Urine sediment microscopy
 
Assess sCr
 
Exclude infection, trauma, bleeding from the distal urinary tract/bladder, menstruation
 
Consider bleeding disorder
 

† Corresponds to KDIGO criteria for Acute Kidney Injury

Additional specialized assessments are available to assess renal function or renal pathology.

Whenever a renal event is identified, a detailed patient history and examination are indicated to identify and potentially eliminate risk factors that may have initiated or contributed to the event:

- Blood pressure assessment (after 5-minute rest, with an appropriate cuff size)
- Signs and symptoms like fever, headache, shortness of breath, back or abdominal pain, dysuria or hematuria, dependent or periorbital edema
- Changes in blood pressure, body weight, fluid intake, voiding pattern, or urine output

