7.1.1 Descriptive analyses

Subject demographics and other baseline characteristics

All data for background and demographic variables will be listed by treatment group and subject. Summary statistics will be provided by treatment group.

Relevant medical history, current medical conditions, results of laboratory screens, drug tests and any other relevant information will be listed by treatment group and subject.

Treatment

Data for study drug administration (rescue medication) and concomitant therapies will be listed by treatment group and subject.

Vital signs

All vital signs data will be listed by treatment, subject, and visit/time and if ranges are available abnormalities (and relevant orthostatic changes) will be flagged. Summary statistics will be provided by treatment and visit/time.

The below descriptive analysis will be conducted on the following two blood pressure (BP) parameters and their change from baseline: SBP and DBP.

- A separate summary statistics (quantitative) of raw values and change from baseline values will be provided by treatment group and timepoint.
- Summary tables of categorical analyses will be produced displaying the number and percentage of subjects with notable BP observations (irrespective of the timepoint) using the following categories:
 - SBP <90 mmHg;
 - SBP >140 mmHg;
 - SBP increase from baseline >20 mmHg;
 - SBP decrease from baseline >20 mmHg;
 - DBP <50 mmHg; DBP >90 mmHg;
 - DBP increase from baseline >20 mmHg;
 - DBP decrease from baseline >20 mmHg

These categorical analyses will be provided for each treatment group

Commercially Confidential Information

For criteria with change from baseline, only measurements occurring after 1st injection on Day 1 will be included. For other criteria, both baseline and post-baseline measurements will be included. All scheduled and unscheduled visits will be used for this summary table.

ECG evaluations

All ECG data will be listed by treatment, subject and visit/time, abnormalities will be flagged. Summary statistics will be provided by treatment and visit/time.

Clinical laboratory evaluations

All laboratory data will be listed by treatment, subject, and visit/time and if normal ranges are available abnormalities will be flagged. A separate listing is provided presenting all parameters in a subject with any abnormal values. Summary statistics will be provided by treatment and visit/time.

Adverse events

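### The planned low/normal/high laboratory shift does not match the protocol's own creatinine and liver-test thresholds, and no readable table counts by arm the subjects who cross them

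*Protocol*

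**What the plan says.** The laboratory paragraph of Protocol 12.5.2 reads as complete. It plans three outputs, presented by treatment group like all safety tables:

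- listings and visit summaries: "if normal ranges are available abnormalities will be flagged. Summary statistics will be provided by treatment and visit/time"
- a shift table: "Shift tables using the low/normal/high/ (low and high) classification will be used to compare baseline to the worst on-treatment value"

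The corresponding paragraph of SAP 7.1.1 plans flagged listings and then: "A separate listing is provided presenting all parameters in a subject with any abnormal values. Summary statistics will be provided by treatment and visit/time". It mentions neither a shift table nor any threshold count.

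Elsewhere the protocol sets numeric laboratory thresholds. Section 10.2.2 defines the renal trigger as a creatinine rise of 25% or more, "compared to baseline during normal hydration status". Table 16-3 divides this into 25–49% ("Confirmed serum creatinine increase") and 50% or more, and adds dipstick protein and blood at 3+ or above. Tables 16-1 and 16-2 set liver thresholds at multiples of ULN: ALT or AST above 3x and 5x, total bilirubin (TBL) above 1.5x and 2x, and ALP above 2x. Section 10.2.1 applies the liver categories "irrespective of whether classified/reported as AE/SAE".

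**The concern.** A normal-range shift asks whether a value moved across a reference limit. The renal thresholds ask how far creatinine moved from the subject's own baseline, and the liver thresholds ask how far above ULN a value went. The shift table answers neither question. It can look clean for creatinine when subjects have met the protocol's 50% criterion, and for ALT it cannot separate a trivial elevation from one that requires action under Table 16-2.

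Safety and tolerability is a secondary objective, and the study is meant to guide later trials. A reader of the report would want to know how many subjects per arm reached the levels that the protocol itself chose to watch. No readable output gives that number.

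**Working it through.** The plan states no figure to reproduce, so the check compares the definitions directly.

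**Creatinine.** Inputs: the 25% and 50% rises (Section 10.2.2, Table 16-3) and the normal category of the shift table (Section 12.5.2). A k-fold rise stays normal when baseline x k ≤ ULN, that is, when baseline ≤ ULN/k.

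- 50% rise: ULN/1.5 = 0.667 x ULN
- 25% rise: ULN/1.25 = 0.80 x ULN

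Any subject with a normal baseline at or below these limits is shown as normal to normal. The SAP's listing of subjects with abnormal values need not include such a subject either. These limits need no outside figure.

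How much of the normal range they cover depends on R = ULN/LLN (LLN is the lower limit of normal), which the documents do not give. The share of the range width is (R/k − 1)/(R − 1). For example, with R = 2.0 and k = 1.5 it is (1.333 − 1)/1 = 33%.

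| R (assumed) | 50% rise stays normal | 25% rise stays normal |
|---|---|---|
| 1.67 | 17% | 50% |
| 1.8 | 25% | 55% |
| 2.0 | 33% | 60% |
| 2.5 | 44% | 67% |

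At R = 1.5 or below, a 50% rise from within the range cannot end below ULN, and the first share is zero. These are shares of the width of the range, not of subjects.

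**Liver tests.** Inputs: Tables 16-1 and 16-2.

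| ALT or AST | Shift category | Protocol level |
|---|---|---|
| 1.1 x ULN | high | none |
| 3.1 x ULN | high | laboratory trigger (if asymptomatic) |
| 5.1 x ULN | high | liver event |
| 10 x ULN | high | liver event |

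A subject already high at baseline shows no shift, whatever the later rise.

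**Other outputs by arm.** Visit summaries do not use the normal range, but they do not count subjects who cross a threshold. The AE tables depend on Section 10.1.1: "Abnormal laboratory values or test results constitute adverse events only if they fulfill at least one of the following criteria". The criteria are signs or symptoms, clinical significance, or a need for therapy. An asymptomatic threshold crossing may therefore never become an AE, and Section 10.2.1 expressly separates the liver categories from AE reporting. Section 12.5.2 plans AE summaries by SMQ (standardized MedDRA query) but names no hepatic or renal one.

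**Contrast.** SAP 7.1.1 does plan the number and percentage of subjects per treatment group with notable blood pressure, including systolic and diastolic changes of more than 20 mmHg from baseline. The same approach is not applied to creatinine or liver tests.

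**The case against.** A reader might infer that these events are never counted by arm, or that the laboratory data are analysed only against the normal range. Neither inference is supported.

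- Summary statistics by treatment and visit are planned, and all laboratory data are to be listed by treatment group and subject. With about 66 subjects in up to six arms, reading the listings is practical.
- Section 10.1.1 tells investigators to look for significant changes from baseline when identifying clinically significant values. A creatinine rise inside the normal range can therefore become an AE and be tabulated by arm.
- Table 16-2 requires treatment to stop for the most serious liver findings. Section 12.3 summarizes reasons for discontinuation by treatment group, and Section 12.5.2 separately summarizes AEs leading to discontinuation.
- Tables 16-1 and 16-3 are monitoring criteria and not endpoints. The plan promises no count of them and so contradicts nothing.
- Parts of the SAP are redacted, including the list of tables, some first-results safety outputs, a block after the blood pressure categories, and Section 7.3. The absence of such a table elsewhere cannot be fully verified.
- Several definitions cannot be derived from routine laboratory data. The renal ones need confirmation, normal hydration, or exclusion of causes such as infection or trauma. Some liver ones need exclusion of bone pathology or Gilbert syndrome, or a mainly conjugated bilirubin fraction. INR and urine protein-creatinine ratio are not in the Table 8-2 panel.

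All of this stands. It limits the size of the gap and the scope of the fix. It does not supply a systematic count, because the AE route depends on investigator judgement and the discontinuation route covers only some liver criteria and does not name them.

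**Conclusion.** The point holds as a minor, inexpensive improvement. The only categorical laboratory analysis by arm in the readable text is the protocol's normal-range shift, which the SAP paragraph does not carry forward. It cannot register a 50% creatinine rise from a normal baseline at or below 0.667 x ULN, or a 25% rise from 0.80 x ULN or below, and it merges every ALT or AST elevation into one category. The other outputs give a partial trace without a systematic count.

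The 0.667 and 0.80 limits are exact. The shares of 17–44% (50% rise) and 50–67% (25% rise) assume R between 1.67 and 2.5. A reader might take them as the proportion of subjects who would be missed. They are not, because the documents give neither a reference range nor a baseline creatinine distribution. The SAP's silence on the shift table also does not show that it was deliberately dropped. The conclusion rests on laboratory paragraphs that show no redaction.

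**What to change.** In Protocol 12.5.2 and SAP 7.1.1, add one table of the number and percentage of subjects per treatment group who reach each of these at any time in the on-treatment period already defined:

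- creatinine increase from baseline of 25–49%, and of 50% or more
- ALT or AST above 3x and above 5x ULN
- TBL above 1.5x and above 2x ULN
- ALP above 2x ULN
- ALT or AST above 3x with TBL above 2x ULN
- new dipstick protein or blood of 3+ or more

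Derive it from the laboratory data and not from AE reports. Label it as laboratory threshold crossings and not as adjudicated renal or liver events, since confirmation and clinical exclusions are not applied. Leave out criteria that need INR or urine protein-creatinine ratio. State in the SAP whether the protocol's shift table will be produced.

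The tests are already in Table 8-2, so the cost is one derived table and a few sentences. The downside is small counts per arm. No clinical rule changes.

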### **Other safety evaluations**

Sheehan suicidality scale score data will be listed by treatment, subject and visit/time; abnormalities will be flagged. Summary statistics will be provided by treatment and visit/time as appropriate.

### **12.5.3 Pharmacokinetics**

Commercially Confidential Information

#### **12.5.4 PK/PD relationships**

Exposure-response analyses will be carried out for relevant endpoints measured in this study.

#### **12.5.5 Patient reported outcomes**

Not Applicable.

### **12.6 Analysis of exploratory endpoints**

Commercially Confidential Information

#### **12.6.3 Other Exploratory Endpoints**

Commercially Confidential Information

### **12.7 Interim analyses**

Commercially Confidential Information

## **12.8 Sample size calculation**

### **12.8.1 Primary endpoint(s)**

Commercially Confidential Information

### **12.8.2 Secondary endpoint(s)**

Not Applicable.

## **13 Ethical considerations and administrative procedures**

### **13.1 Regulatory and ethical compliance**

This clinical study was designed and shall be implemented, executed and reported in accordance with the ICH Harmonized Tripartite Guidelines for Good Clinical Practice, with applicable local regulations (including European Directive 2001/20/EC, US CFR 21), and with the ethical principles laid down in the Declaration of Helsinki.

### **13.2 Responsibilities of the investigator and IRB/IEC**

Before initiating a trial, the investigator/institution must obtain approval/favorable opinion from the Institutional Review Board/Independent Ethics Committee (IRB/IEC) for the trial protocol, written informed consent form, consent form updates, subject recruitment procedures (e.g., advertisements) and any other written information to be provided to subjects. Prior to study start, the investigator is required to sign a protocol signature page confirming his/her agreement to conduct the study in accordance with these documents and all of the instructions and procedures found in this protocol and to give access to all relevant data and records to Novartis monitors, auditors, Novartis Quality Assurance representatives, designated agents of Novartis, IRBs/IECs, and regulatory authorities as required. If an inspection of the clinical site is requested by a regulatory authority, the investigator must inform Novartis immediately that this request has been made.

### **13.3 Publication of study protocol and results**

The protocol will be registered in a publicly accessible database such as [clinicaltrials.gov](http://clinicaltrials.gov) and as required in EudraCT. In addition, after study completion (defined as last patient last visit) and finalization of the study report the results of this trial will be submitted for publication and posted in a publicly accessible database of clinical trial results, such as the Novartis clinical trial results website and all required Health Authority websites (e.g. [Clinicaltrials.gov](http://Clinicaltrials.gov), EudraCT etc.).

For details on the Novartis publication policy including authorship criteria, please refer to the Novartis publication policy training materials that were provided to you at the trial investigator meetings

